6.9.2.5 Relationship between SCD-044 plasma concentrations and efficacy/PD endpoints

subjects with intercurrent events prior to the analysis timepoint will be excluded from the analysis.

6.11 Analyses of PD biomarkers

At the study visits 2, 9, 10, 17 (study weeks 0, 12, 16, and 32), and Early Discontinuation visits occurring before visit 17, a blood sample will be collected for testing of: cytokines in plasma/serum

Additional biomarkers may be included during the study.

Biomarker concentrations and their changes from baseline will be summarized descriptively by visit and treatment group.

6.12 Safety Analyses

All safety analyses will be performed on the Safety population.

6.12.1 Adverse Events

Adverse events will be coded using MedDRA, Version 25.0, AE coding system for purposes of summarization.

An AE will be considered as treatment-emergent (TEAE) if the date of onset is on or after the date of the first study drug administration. AEs with unknown start dates will be counted as treatment-emergent unless the AE resolution date is prior to the study drug start date. If the start date is partially missing, the AE will be considered treatment-emergent, unless the month and year (when available) rule out the possibility that the event occurred post start of study drug dosing.

A TEAE is defined as treatment-related if its relationship to study medication is recorded as “Possible”, “Probable” or “Definite” on the eCRF. In case the relatedness was not assessed, the most conservative result (related) will be chosen for the analysis.

Cardiovascular AEs will be defined as AEs with MedDRA system organ class “Cardiac disorders” or “Vascular disorders”.

Adverse events that are of special interest, that represent signs/symptoms of Progressive Multifocal Leukoencephalopathy (PML) or of Posterior Reversible Encephalopathy Syndrome (PRES) and that are cardiac arrhythmias will be marked on the eCRF.

Events will be assigned to Part I or Part II of the study based on the date of onset, i.e. AEs that start prior to the first dose of the Part II treatment will be assigned to Part I and AEs that start on or after the date of the first Part II dose will be assigned to Part II.

In summaries of TEAEs a subject experiencing the same AE multiple times on the same treatment will only be counted once for that preferred term and treatment. Similarly, if a subject experiences multiple AEs within the same system organ class on the same treatment that subject will be counted only once in that system organ class and treatment. When summarizing AEs by severity, only the most severe occurrence within the preferred term or system organ class and treatment will be used. Similarly, when summarizing AEs by relationship to study drug, only the most related occurrence within the preferred term or system organ class and treatment will be selected for displays in summary tables.

All AE summaries will be presented in 3 ways:

1. For events in Part I only, using Part I treatment groups, with the additional groups SCD-044 Any Dose (including the three SCD-044 groups) and Total (including all subjects).
2. For events in Part II only, using Part II treatment groups, with the additional group Total.
3. For the entire study only for subjects initially randomized to SCD-044 and thus staying on the same treatment throughout the study, using the three active treatment groups with the additional group Total.

An overall summary for the Safety population will include, by treatment and overall, the number and percentage of subjects reporting at least 1 TEAE in the following categories:

- Any TEAE
- Treatment-related TEAE
- Serious TEAE
- Serious drug-related TEAE
- TEAE leading to discontinuation of the study medication
- Treatment-related TEAE leading to discontinuation of the study medication
- TEAE requiring temporary interruption of the study medication
- Treatment-related TEAE requiring temporary interruption of the study medication
- TEAE leading to death.
- TEAEs of special interest

Additional overall summary of cardiovascular TEAEs will include, by treatment and overall, the number and percentage of subjects reporting at least one cardiovascular TEAE in the following categories:

- Any cardiovascular TEAE
- Treatment-related cardiovascular TEAE
- Serious cardiovascular TEAE
- Cardiovascular TEAE leading to discontinuation of the study medication
- Cardiovascular TEAE leading to death.
- Cardiovascular TEAEs of special interest
- Cardiac arrhythmias

The following TEAE frequency tables will be prepared summarizing the number and percentage of subjects reporting at least one TEAE by MedDRA System Organ Class (SOC) and preferred term PT, by treatment group for the Safety population:

- All TEAEs
- Serious TEAEs
- Treatment-related TEAEs
- Serious treatment-related TEAEs
- TEAEs leading to discontinuation of the study medication
- Treatment-related TEAEs leading to discontinuation of the study medication
- TEAE requiring temporary interruption of the study medication
- Treatment-related TEAE requiring temporary interruption of the study medication
- TEAEs occurring in $\geq 2\%$ in any treatment group
- TEAEs of special interest
- Cardiac arrhythmias
- TEAEs with onset during the [REDACTED] period in Part I and in Part II
- TEAEs by Severity
- TEAEs by Relationship to Study Drug.

The tables for the [REDACTED] periods will be separated into sections for Week 1, Week 2 and Week 3 of [REDACTED] where the weeks are defined by the dates of the [REDACTED] visits (Week 1, Week 2 and Week 3 for Part I and Week 16, Week 17 and Week 18 for Part II). Only events occurring in each week in the treatment groups still undergoing [REDACTED] (including the Placebo group in

Part I) will be included. In the Part II table three columns will be included: Placebo/SCD-044 █ mg, Placebo/SCD-044 █ mg and Total as only these groups actually undergo █ in Part II.

All information pertaining to adverse events noted during the study will be listed by subject, detailing verbatim, preferred term, system organ class, start date and study day, stop date, intensity, outcome, action taken and causal relationship to the study drug. The adverse event onset will also be shown relative (in number of days) to the date of first administration of the study drug.

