2. Demographics will be collected, including date of birth, gender, race and ethnicity.
3. A compliance with applicable inclusion and exclusion criteria will be reviewed. (See Sections 4.2, 4.3)
4. After confirming the eligibility, the Subject will be assigned a screening number.
5. A complete medical history will be obtained for the Subject's current and past medical conditions. Significant medical history should include, but not be limited to, evidence of hypertension, lipid disorders, obesity*, heart attack, stroke, congestive heart failure, kidney disease, and auto immune disease and diabetes. Significant surgical history should include, but not be limited to, removal of blockage from an artery and gallbladder removal. (See Section 5.1)

* Obesity = BMI ≥ 30 (as defined by Metropolitan Life Insurance Company Chart)

6. A complete list of current and past (within the previous 30 days) medications will be obtained for each Subject. (See Section 5.8)
7. A physical examination will be performed. At a minimum, the physical examination will include the following: height, weight, assessment of general appearance, comprehensive skin examination, HEENT, heart, lungs, musculoskeletal system, lymph nodes, neurological systems, abdomen, and extremities. (See Section 5.2)
8. A urinalysis dipstick will be performed and evaluated at a site (See Section 5.5)
9. Vital signs (blood pressure, pulse, respiratory rate and oral body temperature) will be documented. Subjects must remain in a seated or supine position for at least 5 minutes before vital signs are obtained. (See Section 5.3)
10. Blood samples will be collected for Hematology, Lipid Profile, Chemistry, Coagulation profile, Serology, QuantiFERON Gold test, and Serum pregnancy test for women of childbearing potential (See Section 5.5)
11. Any AEs occurring after signing Informed Consent should be reported (See Section 5.9)
12. A query for PML (progressive multifocal leukoencephalopathy) will be performed (See Section 5.10)
13. A query for PRES (Posterior reversible encephalopathy syndrome) will be performed (See Section 5.11)
14. A 12-lead electrocardiogram (ECG) will be performed (See Section 5.12)
15. A pulmonary function test will be performed or scheduled with an external expert (See Section 5.6)
16. An ophthalmologic examination including OCT will be performed or scheduled with an external expert (See Section 5.7)

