9.7 Safety Assessment

Safety Assessments will include vital signs, physical examination, adverse events (AEs), laboratory tests, ECG monitoring, pulmonary function tests, ophthalmologic exams.

The safety of SCD-044 will be evaluated by:

- Incidence, seriousness and severity of all adverse events
- Shifts from baseline in hematology and laboratory tests
- Incidence of AEs of special interest (AESI)

■ [REDACTED]

■ [REDACTED]

[REDACTED]

The extent of exposure will be summarized using descriptive statistics. No inferential analyses are planned.

Incidence of all adverse events reported during the study will be summarized using the MedDRA dictionary by System Organ Class and Preferred Term, by treatment group, severity, and relationship to study drug.

An AE is considered treatment emergent if it was not present prior to the first dose of treatment or, if it was present, it worsened in severity or treatment attribution.

Safety analyses will be performed on the Safety Population. All safety data will be listed by treatment and subject in data listings. AEs will also be summarized by actual dose at time of onset of the AE to account for possible dose reductions over the course of the study.

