8. CHANGES FROM PROTOCOL-SPECIFIED ANALYSES

Handling of intercurrent events is expanded in this SAP. There are no other changes from the protocol-specified analyses.

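### SAP 6.12.1 defines treatment-emergent AEs by onset date alone, omitting the protocol's worsening criterion, and SAP Section 8 does not declare the difference

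*SAP*

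**What the plan says.** Protocol 9.7 gives a two-part definition. An AE is treatment emergent if it was absent before first dose, or, "if it was present, it worsened in severity or treatment attribution".

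SAP 6.12.1 has one part. An AE is "treatment-emergent (TEAE) if the date of onset is on or after the date of the first study drug administration". The sentences that follow deal only with unknown or partly missing start dates. No worsening rule for AEs appears in the readable SAP.

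SAP Section 8 names the expanded handling of intercurrent events as a change and then states: "There are no other changes from the protocol-specified analyses".

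The AE tables are built on the TEAE flag. SAP 6.12.1 introduces them with "The following TEAE frequency tables will be prepared summarizing the number and percentage of subjects reporting at least one TEAE", and the general and cardiovascular overview tables are also counts of TEAEs. Events outside the definition remain in the by-subject listing, whose named fields include "start date and study day, stop date, intensity, outcome, action taken and causal relationship to the study drug".

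AE collection starts before dosing. Under the Screening Visit procedures (Protocol 7.1.1), "Any AEs occurring after signing Informed Consent should be reported".

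On a related matter, Protocol 9.7 also says: "AEs will also be summarized by actual dose at time of onset of the AE to account for possible dose reductions".

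**The concern.** The two documents define the same flag differently, and the section of the SAP meant to record such differences says there is none. Someone programming from the SAP and someone reading the protocol could derive different TEAE counts from the same data.

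The event at risk is specific. It is reported after consent, is still present at first dose, gets worse (or is newly attributed to treatment) on study drug, and keeps its original record and onset date. The protocol's second limb exists to catch it. Under the SAP it would be missing from the summary tables, including those for severity, relationship, seriousness, discontinuation and special interest. Safety and tolerability is a stated objective of this dose-ranging study, so the tables should follow the declared definition.

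**Working it through.** The plan gives no figure to reproduce. The check is to take the possible kinds of event and classify each under both texts.

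| Event | Protocol 9.7 | SAP 6.12.1 |
|---|---|---|
| A. Starts on a day after first dose | TEAE | TEAE |
| B. Starts on a day between consent and first dose, never worsens | Not TEAE | Not TEAE |
| C. As B, but severity worsens on drug, same record and onset date | TEAE | Not TEAE |
| D. As B, but attribution moves from not related to possible, same record | TEAE | Not TEAE |
| E. As C, but the worsening is entered as a new record with its own onset date | TEAE | TEAE |
| F. Condition held in medical history, worsening reported as a new AE after dosing | TEAE | TEAE |
| G. Starts on the dosing day but before the dose, never worsens | Not TEAE | TEAE |

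- **Where the texts part.** Rows C, D and G. In C and D the SAP is narrower. In G it is wider, because it compares dates while the protocol asks whether the event was present before the dose. Row G can occur: at the Baseline Visit (Protocol 7.1.2) AEs are assessed and the first dose is then given in the clinic.
- **What decides whether C matters.** Whether a worsening opens a new record (row E) or updates the old one (row C). Protocol 10.1 asks for the duration and intensity of each episode. Protocol Section 5.9, cited for AE procedures, is not in the readable text, so the recording rule cannot be checked.
- **What decides whether D matters.** Whether a change of attribution is given a new onset date. No readable text says so, and a new-record rule for severity alone would not cover it.
- **Consequence in C and D.** Since the frequency and overview tables in 6.12.1 are TEAE tables, the event appears only in the listing.

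**Scale.** The number of events in rows C, D and G cannot be derived from the documents. Only the weight of one subject can be shown. From about 240 subjects (Protocol 4.1) and the 3:1:1:3 allocation (SAP 3.1):

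- placebo and high dose: 240 × 3/8 = 90 each, so one subject is 1/90 = 1.1 percentage points;
- low and intermediate dose: 240 × 1/8 = 30 each, so one subject is 1/30 = 3.3 percentage points.

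This shows how coarse the Part I table percentages are. It is not an estimate of how many subjects are affected.

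**The case against.** The strongest reply is that the difference may have no practical effect. Protocol 10.1 records intensity by episode, and SAP 6.12.1 expects the same AE to occur more than once in a subject and takes the most severe occurrence. Both are compatible with a worsening being entered as a new event, in which case the date rule captures it. The rule is the same for every Part I arm, and Protocol 9.7 plans no inferential safety analysis. This stands as a limit on the size of the point. It does not remove the point: the readable text does not settle the recording rule, it does not obviously cover a change in attribution, and the two written definitions differ in any case.

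A second reply is that an SAP may refine a protocol. It may, but Section 8 is where the refinement should be declared, and Section 8 denies it.

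A third is that the version page of the supplied protocol was removed. The SAP is written against version 3.0 of April 10, 2023. Nothing readable suggests that the supplied text is another version, but this cannot be confirmed.

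Three stronger readings are tempting and are not supported.

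- **That TEAEs will be under-reported.** The documents show that this can happen, not that it will. In row G the SAP counts more events than the protocol does.
- **That the listing will hide the worsening.** The named fields mention no date of change, but SAP 6.12.1 says that all AE information will be listed, and the shells are a separate document that was not supplied.
- **That the SAP has dropped the summary by actual dose at onset.** The visible table list in 6.12.1 does not show it, and that section describes subjects started on SCD-044 as "thus staying on the same treatment throughout the study" without mentioning dose reductions. The table could still be in the shells. This is a query, not a proven departure.

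**Conclusion.** The point holds as an undeclared inconsistency between protocol and SAP. Protocol 9.7 includes worsening in severity or attribution, SAP 6.12.1 does not, and Section 8 is incorrect in reporting no change beyond intercurrent events. The last statement assumes that the supplied protocol is version 3.0.

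Its effect on the tables is unknown. If every worsening, of severity or attribution, opens a new dated record, no event is lost. If not, the events lost are confined to those recorded between consent and first dose that worsen on study drug and keep their original onset date. Nothing here implies a bias between Part I arms. The correction is small but worth making before the AE tables are run, because it settles which definition those tables use.

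**What to change.** 1. **SAP 6.12.1.** Restore the worsening criterion for both severity and treatment attribution. State how each is identified and dated in the data: by a new record, or by a dated change on the existing one. Say how an event that starts on the dosing day before the dose is classified. If the sponsor intends the date-only rule, keep it, and declare and justify it in Section 8.
2. **SAP Section 8.** Correct the statement to list any difference that remains.
3. **Query.** Confirm that the AE summary by actual dose at onset is in the shells. If it is not, add it to 6.12.1 or declare its omission in Section 8.

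The cost is SAP wording and one derivation rule. If the eCRF holds only one severity or one attribution per event, data queries may be needed to date a worsening. If the answer to the query is that the dose-at-onset summary is missing and wanted, its tables and derivation are extra.

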COVID-19 related protocol deviations will be analyzed to assess whether a protocol amendment or other modifications are needed. The Sponsor together with investigators plan to assess the COVID-19 situation to evaluate the benefit: risk of the study on an ongoing basis.

Changes in study visit schedules, missed visits, or subject discontinuations may lead to missing information (e.g., for protocol-specified procedures). It is important to capture specific information in the subject records that explains the basis of the missing data, including the relationship to COVID-19, for missing protocol-specified information (e.g., from missed study visits or study discontinuations due to COVID-19).

A subset of eligible subjects will participate in photographic evaluation.

Randomization and re-randomization will be stratified by three factors: [REDACTED] Approximately the same number of male and female subjects will be enrolled between treatment groups. [REDACTED] . Approximately the same number of subjects who have prior exposure to biologics therapy for atopic dermatitis will

[figure not shown]
be enrolled between treatment groups.

[figure not shown]
[figure not shown]
The assigned Investigational Product will be administered orally once a day. Subjects will be required to use diaries to document the date of study treatments, any missed treatments, and the occurrence of all adverse events.

The duration of each Subject's participation in the study will be approximately 40 weeks (280 days).

If the Principal Investigator or designee determines that the Subject's condition has worsened to the degree that it is unsafe for the Subject to continue in the study, the Subject may be discontinued from the study as a treatment failure and the Subject may be treated using the standard care.

Subjects with conditions or treatments that may affect cardiovascular safety (e.g. heart rate less than 55 bpm), history of uveitis or history of pulmonary conditions such as active severe respiratory disease (e.g. COPD, tuberculosis or pulmonary fibrosis, severe asthma or asthma requiring regular treatment with oral steroids) will be excluded due to the known mechanism-based AEs within this class which may expose such subjects to unwarranted excess risk for a condition with available alternatives.

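### The cardiovascular adverse-event overview counts only two system organ classes and is not reconciled with the eCRF arrhythmia mark, so it can undercount and can disagree with the arrhythmia table

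*SAP*

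**What the plan says.** All the relevant rules are in SAP 6.12.1.

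- **Coding.** "Adverse events will be coded using MedDRA, Version 25.0, AE coding system for purposes of summarization". The visible text does not say whether only an event's primary class counts or a secondary class as well.
- **Cardiovascular events.** "Cardiovascular AEs will be defined as AEs with MedDRA system organ class" Cardiac disorders or Vascular disorders. No term list, standardised query or eCRF mark is added.
- **Arrhythmias.** Adverse events of special interest, PML or PRES signs "and that are cardiac arrhythmias will be marked on the eCRF". No class condition applies.
- **Cardiovascular overview.** It gives "the number and percentage of subjects reporting at least one cardiovascular TEAE in the following categories", and the last category listed is cardiac arrhythmias.
- **Frequency tables.** "The following TEAE frequency tables will be prepared summarizing the number and percentage of subjects reporting at least one TEAE by MedDRA System Organ Class". This list has its own cardiac arrhythmias table, not limited to the two classes.
- **Listing.** "All information pertaining to adverse events noted during the study will be listed by subject", including verbatim term and class.

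SAP 3.1 shows why the category matters: "Subjects with conditions or treatments that may affect cardiovascular safety (e.g. heart rate less than 55 bpm") are excluded because of adverse events known for the drug class.

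**The concern.** Two rules govern one table and nothing says which prevails. The overview is restricted to events in two classes, while one of its rows is defined by a mark that ignores class. Two programmers could follow the text faithfully and produce different counts.

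The class rule also makes membership depend on how an event is worded and coded. Protocol 10.1 defines an adverse event to include signs, symptoms and abnormal findings as well as diseases. The orthostatic form in Protocol Appendix X prompts for dizziness, weakness, visual changes and pallor alongside pulse and blood pressure, and its procedure mentions syncope. Events recorded as findings or symptoms are therefore to be expected, and some may be coded outside the two classes.

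At stake is the only visible table that presents cardiovascular adverse events as a group, for a mechanism-based risk that the plan takes seriously. Besides the exclusion in SAP 3.1, the SAP contents list a separate visit schedule for subjects at higher risk of bradyarrhythmia, and the SAP tabulates subjects who need monitoring beyond 6 hours.

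**Working it through.** The plan gives no figure that depends on this definition, so there is nothing to reproduce. The check has four steps.

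**1. Where each kind of event appears under the SAP text**

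| Event | Overview: any cardiovascular TEAE | Overview: arrhythmia row | Arrhythmia frequency table | All-TEAE tables and listing |
|---|---|---|---|---|
| Marked arrhythmia, coded in either class | yes | yes | yes | yes |
| Marked arrhythmia, coded elsewhere | no | no if the lead-in is taken literally; yes if the mark decides | yes | yes |
| Unmarked heart-rate, blood-pressure, ECG or syncope event, coded elsewhere | no | no | no | yes |
| Other unmarked event in either class | yes | no | no | yes |

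The second line is the inconsistency. On the literal reading, the overview's arrhythmia row can be smaller than the arrhythmia frequency table. On the other reading those two agree, but the arrhythmia row is no longer a subset of the any-cardiovascular row.

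**2. What one omitted subject is worth**

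Inputs: about 240 subjects (Protocol 4.1), allocated 3:1:1:3 to placebo, low, intermediate and high dose (SAP 3.1).

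- 240 × 3/8 = 90 and 240 × 1/8 = 30, so the planned arms are 90/30/30/90.
- 1/90 = 1.1 percentage points and 1/30 = 3.3 percentage points.

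**3. Illustration with assumed values**

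Let p be the true proportion of subjects with a cardiovascular event. Let s be the share of those subjects whose cardiovascular events are all coded outside the two classes. The overview counts subjects, so a subject is lost only if none of their events qualifies. The overview shows p(1 − s), and the chance that it shows at least one case in an arm of n is 1 − (1 − p(1 − s))^n. The documents give neither p nor s.

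| Assumed p | Assumed s | Expected count, n = 90 | Expected count, n = 30 | Chance of at least one case, n = 30 |
|---|---|---|---|---|
| 5% | 0 | 4.5 | 1.5 | 0.79 |
| 5% | 25% | 3.4 | 1.1 | 0.68 |
| 5% | 75% | 1.1 | 0.4 | 0.31 |
| 10% | 0 | 9.0 | 3.0 | 0.96 |
| 10% | 25% | 6.8 | 2.3 | 0.90 |
| 10% | 75% | 2.3 | 0.8 | 0.53 |

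**4. Effect on a difference between arms**

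The difference shown is p_A(1 − s_A) − p_P(1 − s_P), where A is active and P is placebo. Assume p_A = 10% and p_P = 5%, a true difference of 5 points.

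- s = 25% in both arms: 7.5 − 3.75 = 3.75 points.
- s_A = 75%, s_P = 25%: 2.5 − 3.75 = −1.25 points.
- s_A = 25%, s_P = 75%: 7.5 − 1.25 = 6.25 points.

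Each arm's rate can only fall, but the difference can move either way.

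**The case against.** The strongest reply has five parts.

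- **The coding of individual terms is not shown.** The SAP names the dictionary and version but does not say where heart-rate, blood-pressure, ECG or syncope terms sit. This stands: the placement is an assumption to check, and the size of any undercount is unknown.
- **Nothing is lost from the report.** A reader might infer that such events drop out of the safety results, or that marked arrhythmias miss the table intended for them. The documents do not support that. The events remain in the all-TEAE tables and the by-subject listing, and marked arrhythmias have their own frequency table whatever their class. Only the overview is exposed.
- **Vital signs and ECG may be covered elsewhere.** Protocol 9.7 names both as safety assessments. SAP 6.12.3 and 6.12.4 are not in the public text, so no conclusion can be drawn about how measured abnormalities are summarised.
- **This is ambiguity, not contradiction.** Cardiac arrhythmias is the one overview row not worded as a cardiovascular TEAE, which fits a mark-based row, and the cardiovascular special-interest row is simply the overlap of class and mark. This is fair for the row itself. Even on that reading, though, a marked arrhythmia coded elsewhere is in the arrhythmia row and missing from the total above it.
- **A class rule is prespecified and reproducible.** That is a real merit. A term list fixed under blind keeps it.

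**Conclusion.** The point holds within limits. The two-class definition and the eCRF arrhythmia mark are not reconciled in the cardiovascular overview. Followed as written, a marked arrhythmia coded outside the two classes is absent from the any-cardiovascular row and possibly from its own row, and the overview can disagree with the arrhythmia frequency table. Other cardiovascular findings or symptoms coded elsewhere are also absent from the overview.

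Each subject omitted costs about 1.1 points in a 90-subject arm and 3.3 points in a 30-subject arm, assuming enrolment and allocation as planned. The number omitted depends on MedDRA 25.0 placement, on the primary or secondary class rule, and on how sites word events. None of these is in the visible text, so the claim is that the overview can understate cardiovascular events, not that it will.

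A reader might also infer that the drug-placebo or between-dose difference will be understated. The documents do not support this, because they give no event rates or coding shares by arm, and unequal shares could move the difference either way.

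This concerns descriptive safety reporting only and changes no efficacy test, alpha, power or sample size. It is worth correcting because it affects the summary of a principal mechanism-based risk and the correction is cheap.

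**What to change.** In SAP 6.12.1, define a cardiovascular TEAE as any TEAE that meets at least one of these conditions:

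1. it is coded in Cardiac disorders or Vascular disorders, with a statement of whether primary class alone counts;
2. it is marked on the eCRF as a cardiac arrhythmia;
3. its preferred term is on a list of heart-rate, blood-pressure, ECG and syncope-type terms, checked against MedDRA 25.0 and fixed at blinded review.

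The list must be fixed before the Part I unblinding described in SAP section 7, not merely before the final analysis. Use the same set for every row of the overview in all three presentations (Part I, Part II, whole study). Arrhythmias are then a subset of the any-cardiovascular row, and the arrhythmia row matches the frequency table. Footnote the class-only count so the effect of the wider definition is visible.

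The cost is a few sentences of SAP text, one term list and a small programming change. The downside is that a few non-specific terms may enter and the reported cardiovascular rate may rise in all arms. The footnote lets a reader judge that.
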